5.5.2 Identity of Investigational Product

Information about the ABBV-8E12 and placebo products to be used in this study is presented in [Table 5](#).

Table 5. Identity of Investigational Product

Investigational Product	Mode of Administration	Formulation	Strength
ABBV-8E12	Infusion	Solution for infusion in a vial	300 mg/15 mL 1000 mg/ 10 mL
Placebo	Infusion	0.9% Sodium Chloride Injection/Solution for infusion, 250 mL	N/A

N/A = not applicable

0.9% Sodium Chloride Injection/Solution for Infusion will be administered to those subjects not receiving active ABBV-8E12 and as a vehicle for administration of ABBV-8E12. 0.9% Sodium Chloride Injection/Solution for Infusion will be supplied with commercially available material in either bags or bottles, locally sourced by the sites.

However, if mandated by local regulation, or in the case of exceptional circumstances when sites are unable to procure on their own, AbbVie may supply 0.9% Sodium Chloride Injection/Solution for Infusion if necessary.

5.5.2.1 Packaging and Labeling

ABBV-8E12 will be provided in a glass vial as solution for infusion. One vial will be packaged per carton. Each vial and carton will be labeled with the information necessary per country requirement. Labels must remain affixed to the vial and carton. All blank spaces on the label will be completed by the site staff prior to dispensing to the subjects.

The commercially sourced 0.9% Sodium Chloride Injection/Solution for Infusion will not be labeled as an Investigational Medicinal Product (IMP) prior to the handling by the unblinded pharmacist or qualified designee. Instead, after addition of ABBV-8E12 to the 0.9% Sodium Chloride Injection/Solution for Infusion to be administered in the active arm, it will be labeled with a blinded dispensing label by the unblinded pharmacist or qualified designee as required. 0.9% Sodium Chloride Injection/Solution for Infusion without addition of ABBV-8E12, to be administered in the placebo arm, will be labeled with a blinded dispensing label by the unblinded pharmacist or qualified designee as well. Labels must remain affixed to the material.

If an IMP label on the 0.9% Sodium Chloride Injection/Solution for Infusion is mandated by local agencies, labels may be applied on the overwrap and will be removed by unblinded pharmacist prior to administration.

5.5.2.2 Storage and Disposition of Study Drugs

ABBV-8E12 must be stored at 2° to 8°C/36° to 46°F, must be protected from light and **must not be frozen** at any time.

0.9% Sodium Chloride Injection/Solution for Infusion should be stored per the locally approved commercial label, Summary of Product Characteristics (SmPC) or clinical study label.

A storage temperature log is to be maintained to document proper storage conditions. The refrigerator temperature must be recorded on each business day. All temperature excursions lasting longer than 30 minutes must be reported to the Sponsor immediately using the AbbVie Temperature Excursion Management System (ATEMS). Study medication should be quarantined and not dispensed until AbbVie (ATEMS) deems the medication as acceptable.

Investigational products are for investigational use only, and are to be used only within the context of this study. The study drug supplied for this study must be maintained under adequate security and stored under conditions specified on the label until dispensed for subject use or returned to AbbVie or representative.

5.5.2.3 Preparation/Reconstitution of Dosage Form

The preparation of blinded doses will be performed by the unblinded site pharmacist or qualified designee. The prepared IP (placebo and ABBV-8E12) infusion bags should be covered by the blinding bags before dispensation. Written instructions for the preparation of ABBV-8E12 solutions for infusion will be provided as separate document from the protocol.

5.5.3 Method of Assigning Subjects to Treatment Groups

Prior to enrolling subjects, each site will be provided with a user manual as well as a telephone number and user instructions for the Interactive Voice-Response/Interactive Web-Based (IVR/IWB) system. Each user will receive a code number that will be used in combination with a personal identification number (PIN) to access the system by telephone and a unique username and confidential password to access the system through the internet.

As subjects are screened for the study, the IVR/IWB system will assign each subject a unique 5 digit subject number. The first digit will be 2, the second and third digits will be the site number (01, 02, etc.) and the fourth and fifth digits will be assigned in ascending numerical order at each site.

At the Day 1 visit, each subject will be randomly assigned to a double-blind treatment group through the IVR/IWB system after the site verifies that the subject is eligible to participate in the study. The first dose of study drug will be administered after randomization at the same visit. The randomization schedule will be computer-generated and implemented in IVR/IWB system before the start of the study by the AbbVie Statistical Department.

5.5.4 Selection and Timing of Dose for Each Subject

Selection of the dose for this study is discussed in Section 5.6.4. Each subject will be randomized to one of four cohorts as described in Section 5.5.1. ABBV-8E12 will be administered every 4 weeks via IV infusion at the research site in the morning.

5.5.5 Blinding

Placebo solution will be essentially identical in volume to the ABBV-8E12 solution. The Investigator, study site personnel (except the unblinded pharmacist) and the subject will remain blinded to the treatment throughout the course of the study. The study sponsor will remain blinded; however, a pharmacokineticist will be provided individual pharmacokinetic data from Cohort 1 after 48 weeks of treatment. Subject identification numbers will be changed for the pharmacokinetic analysis to maintain the sponsor blind.

ABBV-8E12 and 0.9% Sodium Chloride Injection/Solution for Infusion (if applicable) will be delivered to the unblinded pharmacist or qualified designee in an open-label format. The unblinded pharmacist or qualified designee will prepare the dosing of ABBV-8E12 (in a blinded manner) following the available preparation instructions as appropriate based on the subject's assigned treatment group. For blinding purposes, identical commercial 0.9% Sodium Chloride Injection/Solution for Infusion bag or bottle will be used in the placebo and ABBV-8E12 arms at each site. The unblinded pharmacist or qualified designee will place a blinding bag over the infusion bag or bottle before dispensation following the written instructions provided as a separate document from the protocol.

For investigational product monitoring, there will be an unblinded clinical research associate (CRA) for verification of unblinded documentation. The unblinding procedure for the unblinded pharmacist/designee and the unblinded CRA will be defined in a separate study-specific document.

The IVR system will be programmed with blind-breaker instructions. The study blind for a subject may be broken, if, in the opinion of the investigator, it is in the subject's best interest to know the study drug assignment.

AbbVie must be notified before breaking the blind, unless identification of the study drug is required for a medical emergency, i.e., situation in which the knowledge or the specific blinded treatment will affect the immediate management of the subject's conditions (e.g., antidote is available). AbbVie must then be notified within 24 hours of the blind being broken. The date and reason that the blind was broken must be recorded in the source documentation and on the eCRF, as applicable.

Unblinding of Data for the Data Monitoring Committee (DMC)

In order to ensure that the DMC will be fully informed, the DMC will be unblinded in its assessment of safety and efficacy data. The DMC will have full access to all data as needed for safety assessment and all data included in interim efficacy analyses. SAS data sets blinded with respect to treatment assignment will be sent to an external statistical center by AbbVie. The study randomization schedules will be sent to an external statistical center under separate cover. The external statistician will generate closed reports that will include unblinded information. While the studies are ongoing, only the DMC and the external statistical center will have access to the closed reports. An AbbVie Internal Executive Review Committee (IERC) may request access to closed reports if the discontinuation of the study, major modifications to the study design, or Phase 3 initiation is recommended by the DMC as outlined in the DMC charter. All other AbbVie personnel will remain blinded to the treatment assignment. The AbbVie Primary Contact for the DMC and the AbbVie IERC members will not be involved in any aspects of the trial or its management.

5.5.6 Treatment Compliance

The investigator or his/her designated and qualified representatives will administer study drug only to subjects enrolled in the study in accordance with the protocol. The study drug must not be used for reasons other than that described in the protocol. Subjects will be supervised at the time of study drug administration.

5.5.7 Drug Accountability

The investigator or his/her representative will verify that study drug supplies are received intact and in the correct amounts. This will be documented by signing and dating the Proof of Receipt or similar document. A current (running) and accurate inventory of study drug will be kept by the investigator and will include shipping invoices and the date on which study drug is administered to the subject. An overall accountability of the study drug will be performed and verified by an unblinded AbbVie monitor throughout the study and at the study site closeout visit. Written instructions for IP accountability requirements will be provided in a separate document from the protocol. Upon completion or termination of the study, all original containers (containing used study drug or containing unused study drug) will be destroyed at site, according to instructions from AbbVie and according to local regulations. For those sites where local destruction of unused study drug is not feasible, sites will return the original containers of unused study drug to AbbVie according to instructions from AbbVie and according to local regulations. Labels must remain attached to the containers.

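### Protocol Section 5.5.7 assigns the running drug inventory to the blinded investigator, in conflict with Section 5.5.5; stock changes read with dosing dates can reveal treatment on some days

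*Protocol*

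**What the plan says.** Protocol Section 5.5.5 sets the blind: "The Investigator, study site personnel (except the unblinded pharmacist) and the subject will remain blinded to the treatment throughout the course of the study". The same section says that ABBV-8E12, and saline where applicable, "will be delivered to the unblinded pharmacist or qualified designee in an open-label format". It also provides an unblinded CRA to verify unblinded documentation.

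Section 5.5.7 covers accountability. The investigator or a representative checks that supplies arrive intact and in the right amounts. The next duty has no delegate: "A current (running) and accurate inventory of study drug will be kept by the investigator and will include shipping invoices", and also "the date on which study drug is administered to the subject". Overall accountability is verified by an unblinded sponsor monitor, and further written instructions sit in a separate document. Used and unused containers are destroyed at the site or returned, with no site role named for those records.

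Section 5.5.2.1 describes the products. For the active arms, "ABBV-8E12 will be provided in a glass vial as solution for infusion. One vial will be packaged per carton". The placebo is "0.9% Sodium Chloride Injection/Solution for Infusion without addition of ABBV-8E12, to be administered in the placebo arm". Section 5.5.2 says the saline "will be supplied with commercially available material in either bags or bottles, locally sourced by the sites", although the sponsor may supply it in exceptional cases. Table 5 lists two active strengths, 300 mg/15 mL and 1000 mg/10 mL.

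**The concern.** A record of open-label stock is placed with a person who must stay blinded. The saline container is the same in every arm at a site, so the ABBV-8E12 vial is what separates active from placebo. An accurate running count of vials, kept beside the dates on which subjects were dosed, therefore holds information about assignment. Shipping invoices would normally cover active vials only, because sites source the saline themselves.

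The investigator's blind matters. The investigator judges the relationship of adverse events to study drug (Section 6.1.3), may discontinue subjects (Section 5.4.1) and supervises, personally or through a designee, the training of raters who join late (Section 5.3.1.1). The primary endpoint, CDR-SB, is scored by a rater from the subject and the study partner. Section 5.6.1 rests its claim of unbiased assessment on the placebo control and the double blind. The SAP plans no analysis that would detect or adjust for loss of the investigator's blind.

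**Working it through.** The plan gives no figure to reproduce. The check has two parts.

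**1. The texts side by side**

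| Item | Section 5.5.5 | Section 5.5.7 |
|---|---|---|
| Investigator's status | Blinded throughout | Not mentioned |
| Who receives ABBV-8E12 | Unblinded pharmacist or qualified designee | Investigator or representative verifies receipt |
| Who keeps inventory, invoices and dates | Not stated | Investigator |
| Who verifies for the sponsor | Unblinded CRA | Unblinded monitor |

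The sponsor's side is firewalled in both sections. The site's own inventory is not.

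**2. What stock changes and dates reveal**

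Inputs: four arms at 1:1:1:1 (Section 5.1) and two vial strengths (Table 5). Assumptions: each dose uses the fewest whole vials, and on any day all combinations of arms are equally likely. Write the stock change as (300 mg vials, 1000 mg vials):

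- placebo (0, 0)
- 300 mg (1, 0)
- 1000 mg (0, 1)
- 2000 mg (0, 2)

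*One subject dosed that day.* The four changes differ, so the arm is identified in 4/4 = 100% of cases. Active against placebo needs only that an active dose draws at least one vial. The exact dose needs the whole-vial assumption.

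*Two subjects dosed that day.* There are 4 × 4 = 16 ordered combinations.

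| Stock change | Combinations that give it | Count | Given subject's active/placebo status known? |
|---|---|---|---|
| (0, 0) | both placebo | 1 | Yes |
| (1, 0) | placebo and 300 | 2 | No |
| (0, 1) | placebo and 1000 | 2 | No |
| (0, 2) | placebo and 2000, or both 1000 | 3 | No |
| (2, 0) | both 300 | 1 | Yes |
| (1, 1) | 300 and 1000 | 2 | Yes |
| (1, 2) | 300 and 2000 | 2 | Yes |
| (0, 3) | 1000 and 2000 | 2 | Yes |
| (0, 4) | both 2000 | 1 | Yes |

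Status known: 1 + 1 + 2 + 2 + 2 + 1 = 9, and 9/16 = 56.25%. Both exact arms known: only (0, 0), (2, 0) and (0, 4), so 3/16 = 18.75%.

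*Three subjects dosed that day.* Of 4³ = 64 combinations, a given subject's status is known in 21 (32.8%) and all exact arms in 3 (4.7%).

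*How common are single-subject days?* The documents give no visit calendar. About 400 subjects over up to 80 sites is 400/80 = 5 per site on average, or more if fewer sites take part. With dosing every 4 weeks, days with only one subject are likely to occur. Each subject has 24 scheduled infusions (Section 5.5.1), and one such day is enough to show active against placebo.

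**The case against.** The best defence is that naming the investigator is shorthand for the site's responsibility. Section 5.5.7 opens with the investigator or a representative, and Section 5.5.6 uses similar wording for giving the drug. Preparation, blinded dispensing labels and the covering of bags all belong to the unblinded pharmacist or designee. Using an unblinded monitor and CRA suggests that accountability records are already treated as unblinded. The separate instructions may say that the pharmacist holds the log. On that reading the two sections can both be followed.

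Part of this stands. The protocol does not say that the investigator keeps the log personally, and a pharmacist keeping it on the investigator's behalf could satisfy both sections. But the inventory sentence names no delegate, and a representative is not required to be unblinded. Nothing bars the investigator from seeing a log for which the investigator is responsible. The separate instructions are not among the documents, so they cannot be assumed to override a stated rule.

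The defence also notes that Section 5.5.7 does not ask for vials to be recorded per subject, and that placebo subjects have dated administrations too. Both are correct, and they limit the size of the problem.

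A reader might also see a second contradiction in Section 5.5.2.1, which says of the active vial and carton labels: "All blank spaces on the label will be completed by the site staff prior to dispensing to the subjects". The documents do not support that reading. Section 5.5.5 counts the unblinded pharmacist among site personnel, so site staff can mean the pharmacist.

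**Conclusion.** The conflict is real. Followed as written, Section 5.5.7 puts information about allocation in the hands of someone whom Section 5.5.5 keeps blinded.

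The exposure is partial. It is complete for active against placebo on single-subject dosing days. It is about 56% for a given subject on two-subject days and about 33% on three-subject days. The last two figures, and any reading of the exact dose, rest on the fewest-whole-vials assumption; the percentages also assume equally likely combinations.

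Two stronger conclusions are tempting. One is that every subject's status could be read after one visit. That would need a log linking vials to subjects, which the protocol does not state. The other is that investigators will be unblinded and the CDR-SB comparison biased beyond repair. The documents do not show that unblinding would occur or reach the raters. Section 5.3.1.1 requires designated, certified raters, with central review of audio recordings for selected scales, and does not say that the investigator rates CDR-SB. The point is a rule that permits a breach of the blind, not evidence of one.

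**What to change.** In Section 5.5.7, make the unblinded pharmacist or a qualified unblinded designee responsible for receipt, shipping invoices, the running inventory and the destruction or return records. State that blinded investigators, raters and other blinded staff have no access to these records until database lock, and that only the unblinded CRA or monitor reviews them. Check that the separate accountability instructions say the same. Naming the unblinded pharmacist or designee in the label sentence of Section 5.5.2.1 would be tidy but is optional.

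The cost is protocol wording plus the ethics committee approval that Section 9.1 requires for amendments. The unblinded pharmacist, CRA and monitor are already in the plan, and nothing changes in dose, schedule, sample size or analysis.

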5.6 Discussion and Justification of Study Design

5.6.1 Discussion of Study Design and Choice of Control Groups

This study is designed to assess the safety and efficacy of ABBV-8E12 in subjects with Early AD for up to 96 weeks. The inclusion of placebo administration and the double blind feature of the study will provide unbiased assessments. There is no anticipated risk to subjects in the placebo group because participating in the study will not prevent subjects from taking approved medications for the treatment of AD. The parallel-group

design with placebo control will provide a well-controlled unbiased assessment of the effect of ABBV-8E12 on clinical outcome measures and potential neuroimaging and CSF biomarkers that are associated with AD disease activity. Toxicity management in the parallel group design is described in Section 6.1.6.

5.6.2 Appropriateness of Measurements

Standard pharmacokinetic, statistical and clinical procedures will be utilized in this study. On-treatment safety evaluations (neurological examinations, adverse event monitoring, ECGs) are scheduled at more frequent intervals for the first 48 subjects enrolled (Cohort 1) to promptly detect potential emerging safety signals.

Overall, choice of instruments to measure key domains of function, cognition, behavior and caregiver distress has been guided by published data on their use in MCI and AD patients. These instruments have shown to be sensitive to the change in Early AD and MCI patients over a period of time.

5.6.3 Suitability of Subject Population

The target population is aimed to be still clinically very mildly affected but demonstrating observable disease burden that can be captured and monitored throughout the trial duration. Confirmation of amyloid load on PET imaging will increase the diagnostic accuracy in the early stages of AD and together with onset of clinical symptoms will increase probability of cognitive decline due to initiation of tau spreading. Several neuropathological studies suggested that at the onset of clinical symptoms tau spreading and aggregation has been already initiated but is still an ongoing and potentially interruptible process.

In the 4-week preclinical mouse toxicology study, the highest dose tested was 250 mg/kg and the corresponding C_{max} and AUC_{0-168h} were 3050 $\mu\text{g/mL}$ and 298,000 $\text{hr}\cdot\mu\text{g/mL}$ (on Day 22) after 4 doses administered weekly. Assuming the pharmacokinetics of

ABBV-8E12 is linear, the steady-state pharmacokinetic profiles were simulated at 300, 1000, and 2000 mg following monthly administration of ABBV-8E12 based on the pharmacokinetic data from the 25 mg/kg dose group up to Day 56 in the ongoing SAD study in patients with PSP. The predicted safety margin at the dose levels of 300, 1000, and 2000 mg is approximately 18-, 6- and 3-fold, respectively, for both C_{\max} and AUC. In addition, the predicted AUC for a 1000 mg dose administered over 4 months and for a 2000 mg dose administered over 2 months is no greater than the AUC following a single 50 mg/kg dose predicted from the ongoing SAD study in patients with PSP.

Based on pharmacokinetics from the SAD study, it is possible to estimate the percent of tau in CSF that is bound by ABBV-8E12. For this calculation, it is assumed that the CSF concentration for humanized antibodies is 0.2% of the plasma concentration and that the concentration of tau in CSF is 400 pg/mL. Based on the K_D of ABBV-8E12 determined in vitro, 300 mg will lead to approximately 30% – 55% of tau in CSF being bound by the antibody at predicted C_{trough} and C_{\max} values. Similar modeling was performed with 1000 and 2000 mg ABBV-8E12 and estimated that the average tau binding over the 28 day period ranges from approximately 60% – 80% and 75% – 90%, respectively.

6.0 Complaints

A Complaint is any written, electronic, or oral communication that alleges deficiencies related to the physical characteristics, identity, quality, purity, potency, durability, reliability, safety, effectiveness, or performance of a product/device after it is released for distribution.

Complaints associated with any component of this investigational product must be reported to the Sponsor (Section 6.2.2). For adverse events, please refer to Sections 6.1 through 6.1.6. For product complaints, please refer to Section 6.2.

6.1 Medical Complaints

The investigator will monitor each subject for clinical and laboratory evidence of adverse events on a routine basis throughout the study. The investigator will assess and record

any adverse event in detail including the date of onset, event diagnosis (if known) or sign/symptom, severity, time course (end date, ongoing, intermittent), relationship of the adverse event to study drug, and any action(s) taken. For serious adverse events considered as having "no reasonable possibility" of being associated with study drug, the investigator will provide an "Other" cause of the event. For adverse events to be considered intermittent, the events must be of similar nature and severity. Adverse events, whether in response to a query, observed by site personnel, or reported spontaneously by the subject will be recorded.

All adverse events will be followed to a satisfactory conclusion.

